8.3.1.3 PASI score

Absolute and percent change from Baseline in PASI score is defined in Section 8.1.1.1.

The percent of subjects with absolute PASI score ≤ 1 , ≤ 2 , ≤ 3 and ≤ 5 will be presented over time.

8.3.2 IGA response

- IGA response (Clear with at least a 2-category improvement relative to Baseline) is defined when IGA score is zero with at least a 2-category improvement from Baseline at visit timepoint. (Table 8-1).
- IGA response (Clear or Almost Clear with at least 2 category improvement relative to Baseline) is defined as IGA score of clear [0] or almost clear [1] with at least a 2-category improvement from Baseline at visit timepoint.
- Shift from Baseline in IGA score is defined at each Post-Baseline visit timepoint relative to Baseline.
- Scalp-specific IGA response

A static IGA for scalp PSO will be used to assess disease severity on the scalp

All subjects will complete the scalp IGA at Baseline. Only subjects with scalp involvement at Baseline will complete the scalp IGA at the other visits specified in the protocol. Subjects with scalp involvement at Baseline are defined as those with a scalp IGA score >0 at Baseline.

Scalp lesions will be assessed in terms of clinical signs of redness, thickness, and scaliness using a 5-point scale as outlined in Table 8-2 below.

Table 8–2: Scalp IGA

Score	Short Descriptor	Detailed Descriptor
0	Clear	Scalp has no signs of PSO; post-inflammatory hyperpigmentation may be present
1	Almost clear	Scalp has no thickening; normal to pink coloration; no to minimal focal scaling
2	Mild	Scalp has just detectable to mild thickening; pink to light red coloration; predominately fine scaling
3	Moderate	Scalp has clearly distinguishable to moderate thickening; dull to bright red, moderate scaling
4	Severe	Scalp has severe thickening with hard edges; bright to deep dark red coloration; severe/coarse scaling covering almost all or all lesions

Scalp IGA response is defined as clear [0] or almost clear [1] with at least a 2-category improvement from Baseline. For analysis purposes, the evaluation of scalp IGA will be limited to subjects with a Baseline scalp IGA of at least 2. Therefore, if a subject has a score of 2 at Baseline, they can only be considered a responder if their IGA is 0 (thereby meeting the criterion for a 2-category improvement from Baseline). Subjects with a Baseline scalp IGA of 1 will be assessed per the protocol but will not be part of the scalp IGA analysis.

- Palmoplantar Investigator’s Global Assessment (pp-IGA) response

A static IGA for palmoplantar PSO will be used to assess palmoplantar disease severity.

Only subjects with palmoplantar involvement at Baseline will complete the pp-IGA at the other visits specified in the protocol. Subjects with palmoplantar involvement at Baseline are defined as those with a pp-IGA score >0 at Baseline.

Palmoplantar disease will be assessed in terms of clinical signs of redness, thickness, and scaliness using a 5-point scale as outlined in [Table 8–3](#) below.

Table 8–3: Palmoplantar IGA

Score	Short Descriptor	Detailed Descriptor
0	Clear	Palmoplantar has no signs of PSO; post-inflammatory hyperpigmentation may be present
1	Almost clear	Palmoplantar has no thickening; normal to pink coloration; no to minimal focal scaling
2	Mild	Palmoplantar has just detectable to mild thickening; pink to light red coloration; predominately fine scaling
3	Moderate	Palmoplantar has clearly distinguishable to moderate thickening; dull to bright red and clearly distinguishable coloration; moderate scaling
4	Severe	Palmoplantar has severe thickening with hard edges; bright to deep dark red coloration; severe/coarse scaling covering almost all or all lesions; numerous fissures

PSO=psoriasis; pp-IGA=palmoplantar-specific Investigator's Global Assessment

Palmoplantar IGA response is defined as clear [0] or almost clear [1] with at least a 2-category improvement from Baseline. For analysis purposes, the evaluation of pp-IGA will be limited to subjects with a Baseline pp-IGA of at least 2. Therefore, if a subject has a score of 2 at Baseline, they can only be considered a responder if their IGA is 0 (thereby meeting the criterion for a 2-category improvement from Baseline). Subjects with a Baseline pp-IGA of 1 will be assessed per the protocol but will not be part of the palmoplantar IGA analysis.

A line plot of the IGA responder rate over time, by treatment group will be produced.

8.3.3 BSA

- Absolute change from Baseline in the BSA affected by PSO is defined as Post Baseline BSA minus Baseline BSA affected by PSO.
- Percent change from Baseline in BSA affected by PSO is defined as

$$\text{Percent change from Baseline} = 100 \times \frac{\text{Post Baseline BSA} - \text{Baseline BSA}}{\text{Baseline BSA}}$$

The percent of subjects with absolute BSA=0%, ≤1%, ≤3% and ≤5% will be presented over time.

8.3.4 Product of IGA and BSA (IGAxBSA)

- Absolute change from Baseline in the product IGAxBSA is defined as Post Baseline IGAxBSA minus product of Baseline IGAxBSA.
- Percent change from Baseline in the product of IGAxBSA is defined as

$$\text{Percent change from Baseline} = 100 \times \frac{\text{Post Baseline IGAxBSA} - \text{Baseline IGAxBSA}}{\text{Baseline IGAxBSA}}$$

8.3.5 Dermatology Life Quality Index (DLQI)

The DLQI questionnaire is used for subjects with psoriasis and consists of 10-questions. This is validated, quality-of-life questionnaire that covers 6 domains including symptoms and feelings, daily activities, leisure, work and school, personal relationships, and treatment, as assessed over the past week.

The scoring of each answer for the DLQI is as follows:

Table 8–4: Dermatology Life Quality Index

DLQI Scoring	
Response	Score
Very much	3
A lot	2
A little	1
Not at all	0
Not relevant	0
Question unanswered	0
Q7: ‘prevented work or studying’ = yes	3

The DLQI total score is calculated by adding the score of each question. The maximum score is 30, and the minimum score is 0. The higher the score, the more quality of life is impaired.

Meaning of DLQI Scores

0-1 = no effect at all on patient’s life

2-5 = small effect on patient’s life

6-10 = moderate effect on patient’s life

11-20 = very large effect on patient’s life

21-30 = extremely large effect on patient’s life

This categorization will not be utilized in the analysis.

Because Q7 has a sub-question (referred to as Q7a here) after the leading yes/no question, some clarifying rules for scoring are provided:

- If Q7 is marked as “yes”, a score of 3 is given regardless of the responses to Q7a.
- If Q7 is marked as “no”, “not relevant”, or is missing and Q7a is “A lot”, a score of 2 is given.

- If Q7 is marked as “no”, “not relevant”, or is missing and Q7a is “A little”, a score of 1 is given.
- If Q7 is marked as “no”, “not relevant”, or is missing and Q7a is “Not at all”, a score of 0 is given.
- If Q7 is marked as “no” or “not relevant” and Q7a is missing, a score of 0 is given.
- If Q7 is missing and Q7a is missing, Q7 is considered unanswered (see below for details on how this impacts the overall DLQI score).

If 1 question is left unanswered, this is scored 0 and the scores are summed and expressed as usual out of a maximum of 30. If 2 or more questions are left unanswered, the questionnaire is not scored.

A subject is considered to have achieved the minimally clinical important difference (MCID) if their individual improvement from Baseline score is > 4 . A 4-point improvement in the DLQI score (DLQI response) has been reported to be meaningful for the subject (within-subject MCID).

The DLQI related efficacy variables are defined as follows:

- Change from Baseline in DLQI is defined as Post-Baseline DLQI minus Baseline DLQI.
- Percent of subjects achieving a DLQI total score of 0 or 1 is defined as the number of subjects with DLQI absolute score of 0 or 1 divided by the number of subjects in RS.

Percent of subjects achieving a MICD in DLQI is defined as the number of subjects with improvement from Baseline score of 4 or more divided by the number of subjects in RS. Only subjects with a Baseline DLQI of 4 or greater will be considered for this analysis.

8.3.6 Patient’s Global Assessment of Disease Activity (PGADA) for arthritis visual analog scale (VAS)

The PGADA for arthritis VAS will be used to provide an overall evaluation of arthritis disease symptoms. Subjects will respond to the question, “Considering all the ways your arthritis affects you, please mark a vertical line on the scale below to show how you are feeling today,” using a VAS where 0 is “very good, no symptoms” and 100 is “very poor, severe symptoms.”

All subjects will complete the PGADA at Baseline. Subjects with PsA at Baseline (defined as a past medical history of PsA or PASE ≥ 47) will complete the PGADA at the visits specified in the protocol. Change from Baseline in PGADA is defined as Post-Baseline PGADA minus Baseline PGADA.

8.3.7 Patient Global Assessment of PSO

The Patient Global Assessment of PSO is a PSO-specific item in which the subject responds to the multiple-choice question, “How severe are your psoriasis-related symptoms right now?” Possible responses to the question are “no symptoms,” “mild symptoms,” “moderate symptoms,” “severe symptoms,” or “very severe symptoms.”

The Patient Global Assessment of psoriasis will be summarized based on OC as the primary analysis. No imputation is applied.

Shift from Baseline in PGA (Patient Global Assessment) of PSO score is defined to each Post-Baseline visit timepoint relative to Baseline.

8.3.8 Patient Symptom Diary (PSD)

A patient reported outcome (PRO) measure, the Patient Symptom Diary (PSD), will be used to assess key symptoms relevant to subjects with moderate to severe chronic plaque PSO. The electronic (ePRO) diary will be administered on a daily basis from Screening to the end of the Week 24 Visit.

The PSD consists of 14 different items, each measuring an aspect of the disease and its impact on the subject's quality of life. Each item will be scored separately on a 0-10 scale with 0 for no symptom and 10 for very severe or worst symptom. Weekly averages will be derived for each of the 14 items of the Psoriasis Diary up to Week 24. A weekly average is the sum of the scored item over the course of the study week (up to the actual visit date) divided by the number of days on which the item was completed and will be set to missing if four or more daily assessments (irrespective of whether these are consecutive or not) were missing of the corresponding question.

The Baseline value is also based on a weekly average (up to and including the first dose date) and will be computed in the same manner.

In cases where there is more than one diary record completed on a particular day, all available records within the 7-day window (including any double entries on one day) will be used in the calculation of weekly average scores. If this results in having more than 7 available scores to calculate the weekly average, the 7 records closest to the visit will be used. The diary entry completion date/time stamp will be used to determine this.

- Change from Baseline in PSD score is defined as post Baseline PSD score minus Baseline PSD score.
- Percent change from Baseline in PSD score is defined as

$$\text{Percent change from Baseline} = 100 \times \frac{\text{Post Baseline PSD score} - \text{Baseline PSD score}}{\text{Baseline PSD score}}$$

Absolute and percent changes from baseline PSD score for each item will be summarized by visit for each treatment group.

In addition, each of the PSD scores will be characterized in terms of the cumulative percent of subjects demonstrating a pre-specified point improvement at each visit. The threshold criteria in term of changes from baseline are set to 2.39, 1.98, 2.86, 3.05, 1.99, 2.01, 3.04, 2.82, 2.60, 2.69, 2.68, 1.51, 2.43, and 2.14 respectively for the itch, pain, scaling, redness, burning, cracking, dryness, irritation, sensitivity, lesions, thickening, fatigue, embarrassment, choice of clothing. For this responder analysis, it will be limited to the subjects with a Baseline PSD score at or above the applicable threshold score. Subjects with a missing score will be imputed using NRI.

Cumulative distribution plots will also be provided for absolute change from Baseline PSD at Week 16 for each item.

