from Baseline of 2 would have been met. Therefore, this subject would be considered an IGA 0/1 responder.

Additional ranges of values for other variables are defined in [Table 4–2](#).

Table 4–2: Imputation allowable ranges by variable

Variable	Minimum value	Maximum value	Integer values only
PASI	0	72	No
IGA	0	4	Yes
PSD item	0	10	No
Scalp IGA	0	4	Yes
mNAPSI	0	130	No
BSA	0	100	Yes
IGAxBSA	0	400	Yes
DLQI	0	30	Yes
PGADA	0	100	Yes
SF-36	0	100	No
EQ-5D-3L VAS	0	100	Yes
WPAI dimension scores	0	100	No for variables “Percent work time missed due to problem” and “Percent overall work impairment due to problem”. Yes for variables “Percent impairment while working due to problem” and “Percent activity impairment due to problem” These two variables can only take values that are multiples of 10”
PHQ-9	0	27	Yes

- The Week 16 results from the specified statistical analysis (e.g. stratified CMH, logistic regression) of each of the 100 imputed data sets will be combined for overall inference using Rubin’s rules, which account for the uncertainty associated with the imputed values (Rubin, 1987). This will be done using SAS PROC MIANALYZE.

Note that this procedure indicates that the imputation model will be applied for each treatment group separately in PROC MI, which will be the default method. However, in the event there are computational challenges with the imputation model (eg, due to a standard deviation of 0 for responses of a given imputation), it is acceptable to modify the imputation model to include treatment as a variable in the model rather than running a separate model for each treatment group. It should be noted that doing so assumes that treatment does not interact with any of the other variables in the imputation model.

Some further details about imputation for different analysis sets are provided below:

- Randomized Set: When programming multiple imputation based on the RS, PROC MI will be used with a separate data set for each of the 3 randomized treatment groups (Bimekizumab 320mg Q4W, Bimekizumab 320mg Q8W, Adalimumab). For Bimekizumab 320mg Q4W and Bimekizumab 320mg Q8W, include all scheduled assessment visits from Baseline to Week 56. For the Adalimumab group, include only scheduled assessments from Baseline to Week 24. NOTE: The combined Bimekizumab 320mg group will not be run through PROC MI. The combined group will be obtained by using the imputed values of the individual Q4W and Q8W groups

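### The PSD weekly average is divided by days completed even when double entries add extra records, and the DLQI MCID has two cut-offs and an unclear denominator (SAP 8.3.8 and 8.3.5)

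*SAP*

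**What the plan says.** **PSD (SAP 8.3.8).** There are 14 items. "Each item will be scored separately on a 0-10 scale", and each is reduced to a weekly average: the week's sum "divided by the number of days on which the item was completed". The average "will be set to missing if four or more daily assessments" are absent, so at least 4 completed days are needed. Baseline is derived in the same way. Where a day has more than one diary record, "all available records within the 7-day window (including any double entries on one day) will be used in the calculation of weekly average scores". The rule continues: "If this results in having more than 7 available scores to calculate the weekly average", "the 7 records closest to the visit will be used". No divisor is given for these weeks. The 14 responder analyses use fixed improvement thresholds from 1.51 to 3.05 points (itch 2.39) and are "limited to the subjects with a Baseline PSD score at or above the applicable threshold score". SAP Table 4–2 ("Imputation allowable ranges by variable") gives 0 to 10 for a PSD item, but that table governs imputed values.

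**DLQI (SAP 8.3.5).** The text first says the MCID is reached when improvement is > 4. The next sentence calls a 4-point improvement meaningful to the subject. The variable definition at the end of the section uses an improvement of 4 or more, as do SAP 2.2.1.3 and Protocol 4.3.1. That definition divides by the number of subjects in the Randomized Set (RS), and the following sentence restricts the analysis to Baseline DLQI of at least 4. SAP 3.1 requires the denominator to be displayed but does not settle which one applies here.

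**The concern.** The PSD text counts days in the divisor and in the missingness rule, but counts records in the double-entry rule. Two programmers could both follow the section and obtain different weekly averages, one of them outside the item's scale. Because Baseline and post-Baseline values share the rule, a double entry in either week can change three things: the change score, the responder status, and entry to the responder analysis.

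For DLQI, a subject who improves by exactly 4 points is a responder under one sentence and a non-responder under another, and the choice of denominator changes the reported percentage.

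What is at stake is the reproducibility of secondary-tier summaries. SAP 8.4 attaches nominal Week 16 p-values to the PSD pain, itch and scaling scores, so a reported test could be touched, but none inside the multiplicity procedure.

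**Working it through.** The plan gives no figure of its own to reproduce here; the check is text comparison and arithmetic.

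**PSD inputs (SAP 8.3.8):** completed days d = 4 to 7; records used r, with d ≤ r ≤ 7; item range 0 to 10; thresholds t = 1.51 to 3.05, itch 2.39.

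Literal average = sum/d. Record mean = sum/r. For any non-zero sum the ratio of the two is k = r/d.

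| Completed days | Records | k |
|---|---|---|
| 4 | 5 (one double) | 5/4 = 1.25 |
| 5 | 6 (one double) | 6/5 = 1.20 |
| 6 | 7 (one double) | 7/6 = 1.167 |
| 4 | 7 (maximum) | 7/4 = 1.75 |

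At the maximum, a constant score of 8 gives 7 × 8/4 = 14. With all 7 days completed, the 7-record cap makes the readings agree (7/7) provided all completed days are counted. If only days still represented after the cap were counted, one double entry could give 7/6.

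**Effect on an itch responder (threshold 2.39), 6 records on 5 days:**

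- Double entry at Baseline, constant 5, Week 16 value 3. Baseline is 30/5 = 6.0 or 30/6 = 5.0, so improvement is 3.0 (responder) or 2.0 (non-responder).
- Double entry at Week 16, Baseline 5, records 2, 2, 2, 3, 3, 3. Week 16 is 15/5 = 3.0 or 15/6 = 2.5, so improvement is 2.0 (non-responder) or 2.5 (responder).
- Entry to the analysis, Baseline constant 2. The value is 12/5 = 2.4 (enters) or 12/6 = 2.0 (does not).

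The error can therefore run in either direction.

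**Entry band.** With one double entry, record means from t/k up to t enter only under the literal reading; the width is t − t/k.

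- 4 days: 0.30 to 0.61 points across the 14 thresholds (itch from 2.39/1.25 = 1.91).
- 5 days: 0.25 to 0.51 (itch from 2.39/1.20 = 1.99).
- 6 days: 0.22 to 0.44 (itch from 2.39/1.167 = 2.05).

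**Arm-level effect.** The documents do not say how often double entries occur. Assume that 1% to 10% of weekly averages have one double entry on 4 to 6 completed days, at the same rate in each arm and unrelated to score. Each arm mean is then multiplied by between 1 + 0.01 × 0.167 = 1.0017 and 1 + 0.10 × 0.25 = 1.025, so a between-arm difference changes by about 0.2% to 2.5% of itself.

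**DLQI cut-off.** The score is an integer with minimum 0, so > 4 means at least 5. A subject with Baseline DLQI of 4 passes the Baseline filter but can improve by at most 4 − 0 = 4, and so could never respond under > 4. Under the cut-off of at least 4, every admitted subject can respond.

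**DLQI denominator.** The share with Baseline DLQI below 4 is not given. If it were an assumed 5% to 20%, a rate of 80% among eligible subjects would be reported with RS as denominator as 0.80 × 0.95 = 76% down to 0.80 × 0.80 = 64%. A 20-point arm difference would be reported as 20 × 0.95 = 19 down to 20 × 0.80 = 16 points.

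**The case against.** The day-count divisor can be read as the general rule for the ordinary case of one record per day, with the double-entry paragraph as the specific exception. That paragraph speaks of scores and records as the things being averaged, and a reading that can push an average off the item's scale is hardly a credible rival. The two readings also diverge only when a week has both a double entry and a missed day (provided all completed days are counted). The diary is completed daily within a programmed window (Protocol 9.11), so such weeks may be rare.

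On DLQI, the operative definition and both variable lists say 4 or more, so the intent is clear. A lost ≥ sign in the text conversion cannot be excluded, although the sign reads correctly in the adjacent SAP 8.3.6. The Baseline restriction directly follows the RS definition, and subjects who are not considered would naturally not be counted.

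Much of this stands as an account of intent and size. A per-record mean is the likelier intention, and the denominator point is the weakest of the three. But the only divisor written down is days, and the formula as written produces impossible values. The two DLQI cut-offs contradict each other as the text reads. The RS denominator is named and never restated after the restriction. These are derivation instructions and should not depend on inference.

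**Conclusion.** The concern holds, as a minor one. The PSD divisor is wrong as written for weeks with double entries and 4 to 6 completed days: with one double entry the average is 17% to 25% too high relative to the record mean, and with 7 records on 4 days it is 75% too high. Individual responder status and eligibility can flip. Under the assumed frequencies, with rates equal across arms and unrelated to score, the effect on an arm difference is small.

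For DLQI MCID, the > 4 wording conflicts with the section's own definition, with its Baseline filter, with SAP 2.2.1.3 and with Protocol 4.3.1; the denominator needs stating. The denominator figures rest on an assumed share of subjects below 4 at Baseline.

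Everything affected is an other efficacy variable. No primary or fixed-sequence result depends on it.

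**What to change.** - **SAP 8.3.8:** add, after the double-entry rule: *In weeks with double entries, the sum of the records used (at most 7) is divided by the number of records used.* The average then always stays within 0 to 10. The missingness rule can remain in days.
- **SAP 8.3.5, MCID sentence:** change > 4 to ≥ 4.
- **SAP 8.3.5, MCID percentage:** state the denominator as RS subjects with Baseline DLQI ≥ 4.

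The cost is one new sentence and two wording corrections. No new data are needed and no design feature changes.

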8.3.9 Modified Nail Psoriasis Severity Index (mNAPSI) score

Psoriatic nail disease will be evaluated at the Baseline visit using the mNAPSI. All affected nails will be scored (0 to 3) for onycholysis/oil drop dyschromia, nail plate crumbling, and pitting and will be scored (0 for “no” or 1 for “yes”) for leukonychia, nail bed hyperkeratosis, splinter haemorrhages and red spots in the lunula. The score for an individual nail ranges from 0 to 13 with higher scores indicative of more severe nail disease. The total mNAPSI score is the sum of the scores for each individual nail. If a nail is unaffected, it will be recorded as such and will not contribute to the total mNAPSI score.

If any of the 7 response items that contribute to mNAPSI is present, while other items are missing (ie, partial mNAPSI data), then the missing items are assumed to be 0 for the mNAPSI calculation. In some cases, the data may be captured in such a way that only non-zero component scores are present in the database. Again, those components that are not present are simply assumed to be 0 for the mNAPSI calculation.

Change from Baseline in mNAPSI score for subjects with nail PSO at Baseline is defined as Post-Baseline mNAPSI score minus Baseline mNAPSI.

An mNAPSI75 responder is defined as a subject who achieved at least a 75% improvement from Baseline in the mNAPSI score. mNAPSI90 and mNAPSI100 are defined accordingly. The proportion of mNAPSI75/90/100 responders over time will be summarized for each treatment group.

